## **11.3 Vital Signs Measurements**

### **11.3.1 Definition of variables**

The following vital signs measurements will be taken at the time points specified in the Schedule of Events (refer to the Protocol):

- Heart Rate (beats/min);
- Systolic blood pressure (SBP) (mmHg)
- Diastolic blood pressure (DBP) (mmHg)
- Respiratory rate (breaths/min)
- Temperature (°C)
- Pulse Oximetry (%)
- Overall Investigator Interpretation

### **11.3.2 Biostatistical Methods**

All vital signs data collected at scheduled and unscheduled visits will be included in the listings, but only results collected as scheduled visits will be included in the summary tables.

The parameter names that will be used in the outputs will comprise of the test name and the unit of measure, for example, 'Systolic Blood Pressure (mmHg)'. Parameters will be sorted in the order that the measurements were collected in on the Vital Signs eCRF page within the tables and listings.

The change from baseline to the pre-dose assessment at each post-baseline visit will be calculated for all parameters.

The decimal precision for each parameter will be based on the maximum number of decimals to which the results were reported on the eCRF.

Vital signs measurements will present summary statistics for the results at the baseline and each scheduled post-baseline visit for each of the parameters. In addition, summaries will be presented for the change from baseline values at each scheduled post-baseline visit.

The summary of overall interpretation results table will present counts and percentages for the reported results at baseline and each post-baseline visit/time point. Result categories will be ordered as 'Normal', 'Abnormal not clinical significant (NCS)' and 'Abnormal clinical significant (CS)'.

The listings of vital signs measurements will include all the information collected. In addition, the observations that are used as the baseline record (value) for each parameter will be flagged, and the change from baseline values at each post-baseline visit will be presented.

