6.3. Doses and Schedule of Administration

In the SD arm, subjects will receive one dose of rhu-pGSN or placebo on Day 1 as an IV push at 6 mg/kg.

In the MAD arms, subjects will receive once-daily doses approximately 24 hours apart of rhu-pGSN or placebo on Days 1 through 3 as an IV push at 6, 12, or 24 mg/kg. The first 2 doses

must be administered in the hospital, but the third dose can be given in a monitored outpatient setting where appropriate.

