9.2.2. Vital Signs

Vital signs will include blood pressure, oral temperature, respiration rate, and heart rate, as well as pulse oximetry. Vital signs will be measured during study drug administration at the following time points: predose, at the end of administration, and 30 minutes after the end of administration. Significant findings noticed after the start of study drug that meet the definition of an AE must be recorded in the eCRF.

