### 3. STATISTICAL CONSIDERATIONS

Data will be handled and processed per the sponsor's representative (Novotech) Standard Operating Procedures (SOPs), which are written based on the principles of good clinical practice (GCP).

All data collected on the eCRFs will be presented in the data listings and will be listed and sorted by SD/MAD, treatment, subject number and visit, where applicable. All summaries will present the data by SD/MAD (apart from PK summaries), treatment group and overall (total subjects), as applicable. In addition, all placebo subjects will be combined into a single placebo group for purposes of summarizing the data.

- Continuous variables: Descriptive statistics will include the number of non-missing values (N), mean, standard deviation (SD\*), median, minimum, maximum.  
  
The minimum and maximum values will be displayed to the same decimal precision as the source data, the arithmetic mean, SD\* and median values will be displayed to one more decimal than the source data for the specific variable.  
  
The appropriate precision for derived variables will be determined based on the precision of the data on which the derivations are based, and statistics will be presented in accordance with the abovementioned rules.
- PK data: For PK data the arithmetic mean, standard deviation, median, minimum, maximum, coefficient of variation (CV%), geometric mean and geometric coefficient of variation (geo CV%) values will be presented. For the ratio of concentration data to the (within 30 minutes) pre-dose concentration on Day 1, the  $\ln(\text{SD}^*)$  will also be presented.
- Categorical variables: Descriptive statistics will include frequency counts and percentages per category. Percentages will be rounded to one decimal place, with the denominator being the number of subjects in the relevant population with non-missing data, unless otherwise specified.
- Time to Event Analysis: Through the Kaplan-Meier method, nonparametric estimates of the survivor function will be represented by quartile estimates (Q1, Median and Q3) along with 95 CIs. Product limit estimates will be presented as part of appendices to the study outputs (SAS output).
- Imputation: No missing data will be imputed.
- Baseline: Baseline values will be defined as the last valid, non-missing observation for each subject prior to the first dose of study medication. For the PK analysis, baseline will be defined as the pre-dose value for each study day.

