etc.	Day 1: 30 mins	n	x	x	x	x
		Mean	x.xxx	x.xxx	x.xxx	x.xxx
		Median	x.xxx	x.xxx	x.xxx	x.xxx
		SD	x.xxx	x.xxx	x.xxx	x.xxx
		Minimum	x.xx	x.xx	x.xx	x.xx
		Maximum	x.xx	x.xx	x.xx	x.xx

Note: SD: Standard Deviation

Baseline is defined as the last valid, non-missing assessment prior to first study drug administration. Unscheduled visits not included in post baseline assessments.

Programming Note:  
 Include all Vital Signs Parameters and all time points.

Clinical cut-off date: DDMMYYYY  
 Program: filepath\_name, Output: filepath\_name (version x.x) Created: DDMMYYYY HH:MM

Table 14.3.4.4.2 MAD: Summary of Vital Signs (Summary of Actual and Change from Baseline Values) by Timepoint  
Protocol: BTI-201  
Safety Population

Clinical cut-off date: DDMMYYYY  
Program: filepath\_name, Output: filepath\_name (version x.x) Created: DDMMYYYY HH:MM

Programming Note:  
Repeat Table 14.3.4.4.1  
Include all Vital Sign Parameters and all scheduled time points.  
  
Include: rhu-pGSN 6 mg/kg;  
          rhu-pGSN 12 mg/kg;  
          rhu-pGSN 24 mg/kg;  
          Combined Active;  
          Combined Placebo;  
          Overall

Table 14.3.4.5.1 SD: Summary of Vital Signs Interpretation by Timepoint  
 Protocol: BTI-201  
 Safety Population

Visit		rhu-pGSN: (N=xx)	6 mg/kg	Placebo (N=xx)	Overall (N=xx)
Baseline 	n	xx		xx	xx
	Normal	xx (xx.x%)		xx (xx.x%)	xx (xx.x%)
	Abnormal NCS	xx (xx.x%)		xx (xx.x%)	xx (xx.x%)
	Abnormal CS	xx (xx.x%)		xx (xx.x%)	xx (xx.x%)
Day 1: 30 mins	n	xx		xx	xx
	Normal	xx (xx.x%)		xx (xx.x%)	xx (xx.x%)
	Abnormal NCS	xx (xx.x%)		xx (xx.x%)	xx (xx.x%)
	Abnormal CS	xx (xx.x%)		xx (xx.x%)	xx (xx.x%)
Day 2	n	xx		xx	xx
	Normal	xx (xx.x%)		xx (xx.x%)	xx (xx.x%)
	Abnormal NCS	xx (xx.x%)		xx (xx.x%)	xx (xx.x%)
	Abnormal CS	xx (xx.x%)		xx (xx.x%)	xx (xx.x%)
etc.					

Note: SD: Standard Deviation

Baseline is defined as the last valid, non-missing assessment prior to first study drug administration.  
 NCS = Not Clinically Significant; CS = Clinically Significant.  
 Unscheduled visits not included in post baseline assessments.

Clinical cut-off date: DDMMYYYY  
 Program: filepath\_name, Output: filepath\_name (version x.x) Created: DDMMYYYY HH:MM

Table 14.3.4.5.2 MAD: Summary of Vital Signs Interpretation by Timepoint  
Protocol: BTI-201  
Safety Population

Clinical cut-off date: DDMMYYYY  
Program: filepath\_name, Output: filepath\_name (version x.x) Created: DDMMYYYY HH:MM

Programming Note:  

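### For the second and third MAD injections, the only planned vital-sign change is from the value before the first dose, so it combines any acute injection effect with drift since Day 1

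*SAP*

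**What the plan says.** **Collection.** Protocol 9.2.2 times the vital signs around each administration: "predose, at the end of administration, and 30 minutes after the end of administration". Protocol 6.3 sets repeated dosing: "In the MAD arms, subjects will receive once-daily doses approximately 24 hours apart", on Days 1 to 3.

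**Baseline.** SAP section 3 states: "Baseline values will be defined as the last valid, non-missing observation for each subject prior to the first dose of study medication". It makes one exception: "For the PK analysis, baseline will be defined as the pre-dose value for each study day".

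**Change, methods text.** SAP 11.3.2 states: "The change from baseline to the pre-dose assessment at each post-baseline visit will be calculated for all parameters". It adds: "In addition, summaries will be presented for the change from baseline values at each scheduled post-baseline visit".

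**Change, mock outputs.** Mock Table 14.3.4.4.1 (single dose) has an actual-value column and a change-from-baseline column, with rows for Day 1 end of infusion and Day 1 at 30 minutes. Its footnote reads: "Baseline is defined as the last valid, non-missing assessment prior to first study drug administration". The multiple-dose version, Table 14.3.4.4.2, repeats that shell with the instruction "Include all Vital Sign Parameters and all scheduled time points". Listing 16.2.9.1, repeated for MAD as 16.2.9.2, uses the same single baseline.

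**The concern.** Readings taken just before an IV push, at its end and half an hour later are suited to showing the acute response to that push. For the first dose, the baseline is normally the Day 1 pre-dose reading, so the mock tables' change column shows that response directly. For the second and third doses it does not. The reference is one or two days old, and the subject has been under treatment for pneumonia since then.

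The recommended (not mandatory) diagnostic guidance in Protocol 7.2 lists fever, tachycardia and tachypnea, so abnormal starting values that later settle are plausible. A rise on repeat dosing could then be tabulated as a small change, or as none. Safety and tolerability of multiple ascending doses is part of the primary objective, and the repeat doses are where this summary is least informative.

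The methods text and the mock tables also disagree on which changes are computed. Read literally, the text stops at the pre-dose reading of each later visit and leaves out every post-injection reading.

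**Working it through.** The plan states no figure for vital-sign change, so there is none to reproduce. The check has four steps.

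**1. How many injections are affected.** Each cohort has 6 active subjects, with one single-dose and three multiple-dose cohorts (SAP 2.1).
- Active injections: 6 × 1 + 18 × 3 = 60, of which 54 are in MAD.
- Day 2 and Day 3 injections: 18 × 2 = 36.
- Shares: 36/60 = 60%; 36/54 = 67%.

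**2. What the change column measures.** Let B be the value before the first dose, P that day's pre-dose value and E a post-injection value. Then E − B = (E − P) + (P − B), which is the acute effect plus the drift since Day 1. On Day 1, P is normally B and the drift term is zero. On Days 2 and 3 it is not zero in general. This is an identity and needs no assumption.

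**3. Illustrative size.** The documents give no drift, SD or correlation for any vital sign, so every value in this step is assumed. For heart rate, the tabulated mean change would be:

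| Fall since Day 1 | Acute rise 10 | Acute rise 15 | Acute rise 20 |
|---|---|---|---|
| 0 | 10 | 15 | 20 |
| 10 | 0 | 5 | 10 |
| 20 | −10 | −5 | 0 |

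A same-day reference returns the top row in every case.

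The spread also differs. The SD of a change is σ√(2(1 − ρ)). Take σ = 15:
- First-dose reference, ρ = 0.3 to 0.5: SD 17.7 to 15.0.
- Same-day reference, ρ = 0.8 to 0.9: SD 9.5 to 6.7.
- 90% half-width for the mean at n = 6, 2.015 × SD/√6: 14.6 to 12.3 against 7.8 to 5.5.
- Over σ = 10 to 20, the half-widths span 8.2 to 19.5 against 3.7 to 10.4.

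With σ = 15, ρ = 0.5 and 0.8, and a true mean rise of 20, the share of subjects whose tabulated change is at least 20 is 50% with no drift, 25% with a fall of 10 and 9% with a fall of 20. With a same-day reference it stays at 50%.

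**4. What can be recovered from the planned outputs.**
- *Mean within-day change:* yes, by subtracting two tabulated means, provided the same subjects contribute to both.
- *SD, minimum and maximum of that change:* not from the tables, because these do not follow from the separate summaries of P and E.
- *Individual changes:* yes, by hand from the listings. For active MAD subjects that is 18 subjects × 2 days × 2 post-injection readings × 6 numeric parameters = 432 subtractions.

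**The case against.** The strongest reply is that a reaction remains visible in several places.

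- **Actual values.** The same tables give actual values at every time point. A Day 3 pre-dose mean of 90 and an end-of-administration mean of 110 would both be printed.
- **Placebo.** MAD tables carry Combined Placebo, which shares the illness, standard care, baseline rule and time points. If active subjects show 0 where placebo shows −20, the contrast of 20 is visible.
- **Listings.** With 6 active subjects per cohort, extremes can be found by reading them.
- **Direct capture.** Injection-related reactions are graded (Protocol 6.5.1) and interruptions are listed with reasons (SAP 8). Significant vital-sign findings that meet the adverse-event definition must be recorded (Protocol 9.2.2). Investigator interpretation is tabulated by time point (SAP 11.3.2).
- **Endpoint.** The primary endpoint (Protocol 5.2.1) does not name mean vital-sign change.

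All of this stands, and it confines the problem to the change-from-baseline summaries. Some limits remain. Combined Placebo is 6 subjects, 2 from each cohort, and shows average drift rather than each subject's own. With the assumed SD of 15.0, the standard error of an active-minus-placebo difference is 15.0 × √(1/6 + 1/6) = 8.7; with same-day changes (SD 9.5) it is 5.5. Investigator interpretation classes a reading and does not measure a change.

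The PK comparison should not be pressed. PK uses a daily pre-dose value because the measured concentration is endogenous plus exogenous protein (SAP 9). That shows the per-day derivation is already in use, not that vital signs must follow it.

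The 11.3.2 sentence also recurs for EKG (11.4.2) and outcome scores (11.6.2). It may be template wording rather than a decision to omit post-injection readings.

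**Conclusion.** The point holds as a limited one. For 36 of 60 planned active injections, no output summarises the within-day vital-sign change. The change that is summarised at those post-injection readings contains drift since Day 1. The tables cannot supply the SD, minimum or maximum of the within-day change. The 11.3.2 text and the mock tables also conflict and need reconciling. These conclusions rest on the definitions and the identity alone.

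A reader might infer three stronger things that the documents do not support.
- *Reactions to repeat doses would be hidden from the trial.* They would not; only one column is affected.
- *Vital signs are known to move strongly between Day 1 and Day 3.* No trajectory or spread is given, so the size of any masking is unknown and the figures above are illustrations.
- *60% measures bias or missed reactions.* It counts injections that lack a derived summary.

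A single pre-first-dose baseline is a legitimate descriptive choice and suits Day 1 and the single-dose cohort. The change proposed is a low-cost improvement to the safety summary. It does not correct an error that would invalidate that summary.

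**What to change.** In SAP 11.3.2, Tables 14.3.4.4.1 and 14.3.4.4.2, and Listings 16.2.9.1 and 16.2.9.2:

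1. For each dosing day, add the change from that day's pre-dose value to the end of administration and to 30 minutes afterwards. Summarise it by dose and placebo (Combined Placebo in MAD) with n, mean, SD, median, minimum and maximum, using subjects who have both readings.
2. Keep the change from the pre-first-dose baseline, which still describes the course over the study.
3. Reword the 11.3.2 sentence so that text and mock tables name the same time points.
4. Add the within-day change as a column in the listings.

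The cost is one derived variable, some extra table columns and a few lines of SAP text. All readings are already scheduled; sample size, visits and treatment are unaffected. SAP section 1 allows the analysis to be done post hoc, but specifying it beforehand avoids that label.

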## **11.4 12 - Lead Electrocardiogram (EKG)**

### **11.4.1 Definition of variables**

The following EKG measurements will be taken at the time points specified in the Schedule of Events (refer to the Protocol):

- Heart Rate (beats/min);
- PR Interval (ms)
- QRS Interval (ms)
- QT Interval (sec)
- QTcF Interval (ms) = QT interval /cube root of the RR interval
- Overall Investigator Interpretation

### **11.4.2 Biostatistical Methods**

All EKG data collected at scheduled and unscheduled visits will be included in the listings, but only results collected as scheduled visits will be included in the summary tables.

The parameter names that will be used in the outputs will comprise of the test name and the unit of measure, for example, 'Heart Rate (beats/min)'. Parameters will be sorted in the order that the measurements were collected in on the EKG eCRF page within the tables and listings.

For study visits where, multiple EKG measurement are taken, the mean of the measurements will be summarized and the worst-case overall investigator interpretation for the multiple measurements will be presented.

The change from baseline to the pre-dose assessment at each post-baseline visit will be calculated for all parameters.

The decimal precision for each parameter will be based on the maximum number of decimals to which the results were reported on the eCRF.

EKG measurements will present summary statistics for the results at the baseline and each scheduled post-baseline visit for each of the parameters. In addition, summaries will be presented for the change from baseline values at each scheduled post-baseline visit.

The summary of overall interpretation results table will present counts and percentages for the reported results at baseline and each post-baseline visit/time point. Result categories will be ordered as 'Normal', 'Abnormal NCS' and 'Abnormal CS'.

The listings of EKG measurements will include all the information collected and calculated (mean results). In addition, the observations that are used as the baseline record (value) for each parameter will be flagged, and the change from baseline values at each post-baseline visit will be presented.

## **11.5 Physical Examinations**

Physical Examination assessments will be listed for all time points.

## **11.6 Outcome Prediction Models**

### **11.6.1 Definition of variables**

The following outcome prediction models will be taken at the time points specified in the Schedule of Events (refer to the Protocol):

- CURB-65 Score;

- Pneumonia Severity Index (PSI) Score
- Pneumonia Severity Index (PSI) Risk Class
- SOFA Score
- Mini-Mental State Exam (MMSE) Score

#### **11.6.2 Biostatistical Methods**

All outcome prediction model data collected at scheduled and unscheduled visits will be included in the listings, but only results collected as scheduled visits will be included in the summary tables.

The change from baseline to the pre-dose assessment at each post-baseline visit will be calculated for all parameters.

The decimal precision for each parameter will be based on the maximum number of decimals to which the results were reported on the eCRF.

Outcome prediction model scores will present summary statistics for the results at the baseline and each scheduled post-baseline visit for each of the parameters. In addition, summaries will be presented for the change from baseline values at each scheduled post-baseline visit.

The summary of PSI Risk Class will present counts and percentages for the reported results at baseline and each post-baseline visit/time point. Result categories will be ordered by risk class.

The listings of outcome prediction model data will include all the information collected. In addition, the observations that are used as the baseline record (value) for each parameter will be flagged, and the change from baseline values at each post-baseline visit will be presented.

#### **11.7 Concomitant Medications**

Concomitant and prior medications will be coded using World Health Organization Drug Dictionary (WHO-DD, September 2015).

Prior medications are defined as any medication where the use was stopped prior to the first administration of the study medication. Prior medications will be listed only.

Concomitant medications are defined as any medication (other than the study drug) that was used at least once after the first administration of the study medication. Medications that were stopped on the same date as the first study drug infusion will be analyzed as concomitant medications. If a clear determination cannot be made (partial medication end dates) the medication will be classified as concomitant.

Concomitant medications will be summarized by WHO-DD Anatomical Therapeutic Chemical (ATC) class Level 3, and preferred term using frequency counts and percentages by study part and treatment group. Subjects who take the same medication more than once will be counted only once for that preferred term. Subjects will also only be counted once for each ATC3 class, regardless of the number of medications they have taken within that class

#### **11.8 Other safety evaluations**

Hospitalization follow-up will be presented in by-subject listings by study part and treatment group. Length of stay in hospital defined as date and time of discharge or date of study exit if still hospitalized at the time of death or study exit (censored at 23:59) - date and time of Hospitalization admission due to CAP in hours, length of ICU stay and the period of intubation in days will be listed and presented through Kaplan-Meier (K-M) methods.

The length of stay in ICU and period of intubation analysis will be restricted to subjects that stayed in the ICU and were intubated. The event investigated will be the cessation of ICU stay and the cessation of intubation.

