5.2.3. Exploratory Endpoints

- Baseline and sequential pGSN levels
- Clinical outcomes: 28-day survival; ICU days; days on ventilator or pressers; days on antibiotics; duration of hospitalization; Δ SOFA and CURB-65 scores
- Temporal profiles of inflammatory biomarkers
- Pathogen type (bacterial; viral; other; unknown) determined per customary work-up at each site

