Note: CI = Confidence Interval; Brookmeyer and Crowley method (1982, Log-log transformation);  
 Length of stay in hospital is defined as the date and time of discharge/date of study exit (23:59 PM) -  
 date and time of hospitalization admission due to CAP in hours

Clinical cut-off date: DDMMYYYY  
 Program: filepath\_name, Output: filepath\_name (version x.x) Created: DDMMYYYY HH:MM

Table 14.3.4.13.2 MAD: Summary of Hospitalization  
Protocol: BTI-201  
Safety Population

Clinical cut-off date: DDMMYYYY  
Program: filepath\_name, Output: filepath\_name (version x.x) Created: DDMMYYYY HH:MM

Programming Note:  
Repeat Table 14.3.4.13.1  
Include all scheduled time points.  
  
Include: rhu-pGSN 6 mg/kg;  
          rhu-pGSN 12 mg/kg;  
          rhu-pGSN 24 mg/kg;  
          Combined Active;  
          Combined Placebo;  
          Overall

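### SAP 11.8 censors in-hospital deaths in the length-of-stay analysis and gives no rule for death in the ICU or while intubated, so none of the three durations handles death properly

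*SAP*

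**What the plan says.** Protocol 5.2.3 lists among the exploratory clinical outcomes "ICU days; days on ventilator or pressers; days on antibiotics; duration of hospitalization". The SAP covers these durations in section 11.8.

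- **Hospital stay.** Time runs from admission for CAP to discharge or, without a discharge, to "date of study exit if still hospitalized at the time of death or study exit (censored at 23:59". The shell for Table 14.3.4.13.1 has rows for subjects discharged and not discharged, and its footnote repeats the end point: "Length of stay in hospital is defined as the date and time of discharge/date of study exit (23:59 PM". A subject who dies in hospital is not discharged and is therefore censored.
- **ICU stay and intubation.** "The length of stay in ICU and period of intubation analysis will be restricted to subjects that stayed in the ICU and were intubated", and "The event investigated will be the cessation of ICU stay and the cessation of intubation". Nothing says whether death is a cessation, a censoring or a competing event. The table shell has no event, death or censored counts for these two durations. The notes to Figures 14.3.3.1 to 14.3.4.2 restrict the set of subjects and do not mention death.
- **Estimator.** SAP section 3 names only Kaplan-Meier: "nonparametric estimates of the survivor function will be represented by quartile estimates (Q1, Median and Q3) along with 95 CIs". No competing-risk method is planned.

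Overall survival (SAP 11.1.2), by contrast, has an explicit event and an explicit censoring rule.

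**The concern.** Kaplan-Meier treats a censored subject as someone who would later have had the event at the same rate as those still under observation. A subject who has died will never be discharged. Censoring deaths therefore estimates time to discharge in a setting without deaths, and the curve runs towards everyone being discharged alive whatever the mortality.

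The ICU and intubation analyses have the opposite exposure. Death does end an ICU stay or an intubation, so a programmer following the wording literally would count it as the event, and an early death would become a short, favourable-looking stay. A programmer who carried over the hospital-stay rule would censor it instead. The SAP leaves that choice open, and the two choices give different quartiles from the same data.

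What is at stake is how the clinical outcomes read by dose, which Protocol 5.1.3 sets as an exploratory objective. Active and placebo curves are drawn on one graph, and in arms of about 6 one or two deaths can move a quartile.

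**Working it through.** The documents state no expected stay, mortality or event count for these analyses, so there is no planned figure to reproduce. The check asks how far each treatment of death moves the quartiles under constant hazards.

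**Inputs (assumed).** Hazard of leaving alive λ = 0.17/day; hazard of death δ = 0.01 or 0.06/day. The fatal share of exits is δ/(λ+δ): 0.01/0.18 = 5.6% and 0.06/0.23 = 26%.

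**Formulas for the median**

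- Death censored: ln 2/λ.
- Death as the event (any cessation): ln 2/(λ+δ).
- Death as not discharged (cumulative incidence of leaving alive): the t that solves [λ/(λ+δ)]·[1 − exp(−(λ+δ)t)] = 0.5, so t = −ln[1 − 0.5(λ+δ)/λ]/(λ+δ).

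**Hospital stay**

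- Deaths censored: 0.693/0.17 = 4.1 days; 75th percentile ln 4/0.17 = 8.2 days. Neither depends on δ.
- Death as not discharged, 5.6% fatal: −ln(1 − 0.5 × 0.18/0.17)/0.18 = 0.754/0.18 = 4.2 days.
- Death as not discharged, 26% fatal: −ln(1 − 0.5 × 0.23/0.17)/0.23 = 1.128/0.23 = 4.9 days. The 75th percentile is not reached, because at most 0.17/0.23 = 74% ever leave alive.
- Discharged alive by Day 28 at 26% fatal: the censored analysis implies 1 − exp(−0.17 × 28) = 99%; the cumulative incidence is 0.739 × [1 − exp(−0.23 × 28)] = 74%.

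**ICU stay or intubation, death read as cessation (same hazards for illustration)**

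- 5.6% fatal: 0.693/0.18 = 3.9 days.
- 26% fatal: 0.693/0.23 = 3.0 days.

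**Second scale.** Set the no-death median at 7 days and let m be the fatal share of stays. The any-cessation median is then 7(1 − m), and the cumulative-incidence median is −(1 − m)·ln[1 − 0.5/(1 − m)]·7/ln 2.

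| Fatal share m | Death as event | Death censored | Death as not leaving alive |
|---|---|---|---|
| 10% | 6.3 | 7.0 | 7.4 |
| 20% | 5.6 | 7.0 | 7.9 |
| 30% | 4.9 | 7.0 | 8.9 |
| 40% | 4.2 | 7.0 | 10.9 |

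Counting death as the event shortens the apparent stay, censoring it makes the median insensitive to deaths, and the competing-risk estimate lengthens as mortality rises.

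**The case against.** The strongest reply is that little turns on this. The durations are exploratory and summarised descriptively, with no between-arm test named, in cohorts of 6 active and 2 placebo subjects. Deaths are not lost: they are part of the primary endpoint (Protocol 5.2.1), have their own treatment-emergent tables, and are analysed as overall survival. That stands, and it limits the weight of the point.

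The assumed mortality can also be challenged. Protocol 7.3 excludes subjects who are intubated, on vasopressors or admitted directly to the ICU. The US figures in Protocol 4.1 give a crude ratio of 52,000/1,100,000 = 4.7%, which is not this population's in-hospital mortality but is far below 26%. At 4.7% and λ = 0.17/day the hospital-stay median is 4.17 days against 4.08 with deaths censored, about 2 hours apart. At low mortality the hospital-stay error is therefore small. The fatal share among subjects who reach the ICU or are intubated is unknown and could be higher.

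Four stronger readings are tempting, and the documents support none of them.

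- A reader might infer that the SAP counts death as cessation. It never says so; its text is silent on death there, and that reading is only the literal one.
- A reader might infer that deaths make all three durations look shorter. That describes ICU stay and intubation under the literal reading. For hospital stay, censoring leaves the median where it would be without deaths; it is short only relative to a competing-risk estimate.
- A reader might infer that restricting the analysis to "restricted to subjects that stayed in the ICU and were intubated" hides any effect on needing the ICU. It does not: Table 14.3.4.13.1 gives counts in and not in the ICU, and intubated and not intubated, by arm, and both events are in the primary and secondary endpoints.
- A reader might take Protocol 5.2.3 to require these durations in all subjects. It does not specify the set.

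**Conclusion.** The point holds in two parts. First, the stated rule for length of stay is unsuitable: censoring in-hospital deaths in a Kaplan-Meier analysis yields quartiles that ignore mortality and overstates the probability of discharge alive. Second, ICU stay and intubation have no rule for death; the literal reading scores a fatal stay as a short one and is inconsistent with the hospital-stay rule.

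With λ = 0.17/day, the hospital-stay median is low by about 0.1 day at about 5% fatal exits (4.1 against 4.2) and by 0.8 day at 26% (4.1 against 4.9). The ICU or intubation median, with death as the event, drops by 0.9 day (3.9 to 3.0) as the fatal share goes from 6% to 26%. These sizes rest on constant, assumed hazards. The directions follow from the estimators. The primary safety analysis is unaffected. The change is worth making because it is cheap and because a separate survival table does not correct a misleading ICU or ventilator curve.

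**What to change.** In SAP 11.8:

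1. Define the three events as discharge alive, ICU exit alive and extubation alive.
2. State one rule for death across all three: either a competing event, reported as cumulative incidence, or retention in the risk set to Day 28 as not discharged (or not out of the ICU, or not extubated).
3. Add counts of alive exits, deaths and censored subjects for each duration to Tables 14.3.4.13.1 and 14.3.4.13.2, and carry the rule into the table footnotes and the figure notes.

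A summary of ICU days and ventilator days over all dosed subjects is optional. Its median would be 0 in any arm where most subjects never enter the ICU.

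The cost is SAP wording and minor programming. The downside is that some upper quartiles will be reported as not reached.
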